11.3 Disease Parameters

Measurable disease. Measurable lesions are defined as those that can be accurately measured in at least one dimension (longest diameter to be recorded) as ≥ 20 mm with conventional techniques (CT, MRI, x-ray) or as ≥ 10 mm with spiral CT scan. All tumor measurements must be recorded in millimeters (or decimal fractions of centimeters).

Non-measurable disease. All other lesions (or sites of disease), including small lesions (longest diameter <20 mm with conventional techniques or <10 mm using spiral CT scan), are considered non-measurable disease. Bone lesions, leptomeningeal disease, ascites, pleural/pericardial effusions, lymphangitis cutis/pulmonis, inflammatory breast disease, abdominal masses (not followed by CT or MRI), and cystic lesions are all non-measurable.

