11.5 Response Criteria

11.5.1 Complete Response (CR)

CR requires **all** of the following:

1. **PET positive prior to therapy:** mass of any size permitted if PET negative with a score of 3 or less on the Deauville five point scale.

1-no uptake or no residual uptake

2-slight uptake, but below mediastinal blood pool

3-uptake above mediastinal, but below or equal to uptake in the liver

4-uptake slightly to moderately higher than liver

5-markedly increased uptake or any new lesion

New sites of FDG-avidity felt unrelated to lymphoma (Deauville 3 or less) will be considered CR but imaging should be repeated 6-8 weeks later to insure resolution of inflammatory changes.

2. Variably FDG-avid or PET negative prior to therapy: regression to normal size on CT (≤ 1.5 cm in their greatest transverse diameter for nodes ≥ 1.5 cm before therapy). Previously involved nodes that were 1.1 to 1.5 cm in their greatest transverse diameter before treatment must have decreased to <1 cm in their greatest transverse diameter after treatment, or by more than 75% in the sum of the products of the greatest diameters (SPD).
3. The spleen, if considered to be enlarged before therapy on the basis of a CT scan, must have regressed in size and must not be palpable on physical examination.

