11.5.2 Partial Response (PR)

1. $\geq 50\%$ decrease in SPD of up to 6 largest dominant masses
 - a. FDG-avid or PET positive prior to therapy: one or more PET positive at previously involved site with a Deauville score >3
 - b. Variably FDG-avid or PET negative: regression on CT
2. No new sites of disease or increase in the size of the other nodes, liver, or spleen.
3. Splenic and hepatic nodules must regress by at least 50% in the SPD.

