11.5.3 Stable Disease (SD)

Stable disease is defined as less than a PR (see above) but is not progressive or relapsed disease FDG-avid or PET positive prior to therapy: PET positive at prior sites of disease and no new sites on CT or PET. Variably FDG-avid or PET negative: no change in size of previous lesions on CT

11.5.4 Progressive Disease (PD) or Relapsed Disease (RD):

1. Appearance of a new PET positive (Deauville 4 or 5) lesion(s) > 1.5 cm in any axis, $\geq 50\%$ increase in SPD of more than one node, or $\geq 50\%$ increase in longest diameter of a previously identified node > 1 cm in short axis..
2. $>50\%$ increase from nadir in the SPD of any previous lesions

New sites of FDG-avidity felt unrelated to lymphoma (Deauville 3 or less) not be considered PD or ED, but imaging should be repeated 6-8 weeks later to insure resolution of inflammatory changes.

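### Section 11.5.4 has no progression rule for diffuse spleen or liver enlargement or for worsening non-measurable disease, although organ size is used to deny response

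*Combined protocol and SAP*

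**What the plan says.** All references are to the combined protocol and SAP.

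**Progression (11.5.4).** Item 1 has a new-lesion limb, "Appearance of a new PET positive (Deauville 4 or 5) lesion(s) > 1.5 cm in any axis", and two nodal-growth limbs: a 50% rise in the SPD of more than one node, or a 50% "increase in longest diameter of a previously identified node > 1 cm in short axis". Item 2 is a rise of more than 50%, "increase from nadir in the SPD of any previous lesions".

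**Response.** For CR, 11.5.1 item 3 states: "The spleen, if considered to be enlarged before therapy on the basis of a CT scan, must have regressed in size". For PR, 11.5.2 item 2 requires: "No new sites of disease or increase in the size of the other nodes, liver, or spleen". Item 3 of the same section adds: "Splenic and hepatic nodules must regress by at least 50% in the SPD".

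**Stable disease (11.5.3).** This is the residual class: "Stable disease is defined as less than a PR (see above) but is not progressive or relapsed disease".

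**Non-measurable disease (11.3).** The list includes "Bone lesions, leptomeningeal disease, ascites, pleural/pericardial effusions, lymphangitis cutis/pulmonis, inflammatory breast disease", among others.

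**Endpoints.** Duration of response (11.6) ends at objectively documented recurrence or progression. PFS (11.7) ends at documented progression or death. Both are secondary (1.3, 13.1).

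**Governing criteria.** Sections 11.1 and 13.1 refer to the 2014 lymphoma response criteria. Section 11.2 sends classification of response to the definitions that follow it in the protocol.

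**The concern.** The response rules treat an enlarging spleen or liver as evidence about the lymphoma, but the progression rule does not. Existing non-measurable disease is named in 11.3 and then plays no part in 11.5.4.

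The practical effect is on event dating. Take a responder whose nodes stay small while the spleen re-enlarges diffusely. That subject no longer meets the PR conditions but has no progression event under the written text. Duration of response continues until a node or measurable lesion grows or a new PET-positive lesion appears. PFS continues until one of those or death. The same label feeds the rule in 5.1 that gives cycle 2 to subjects without progression, and the off-therapy criteria in 5.4.

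**Working it through.** **1. Which kinds of worsening meet a limb of 11.5.4?**

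| Worsening, with nothing else changed | Item 1, new lesion | Item 1, nodes | Item 2, SPD | Progression as written? |
|---|---|---|---|---|
| Existing splenic or hepatic nodule, SPD up more than 50% from nadir | no | no | yes | yes |
| New PET-positive lesion over 1.5 cm, any organ | yes | no | no | yes |
| Diffuse spleen or liver enlargement, no measurable lesion | no | no | no SPD | no |
| Existing bone lesion, effusion or ascites worsens | no | no | no SPD | no |

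Row 1 follows because item 2 is not limited to nodes and 11.5.2 item 3 measures such nodules by SPD. Row 2 follows because the new-lesion limb has no organ restriction.

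**2. How is a subject in row 3 or 4 classed?** With no other change there is no regression to support CR or PR, and in row 3 the organ growth itself bars PR. No progression limb is met. The residual definition in 11.5.3 then gives stable disease.

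**3. The plan's own figures.** The only design calculation is the Simon design for ORR in 13.2: 13 subjects, continue with 6 or more responses; 28 in total, success with 15 or more. With X₁ the stage 1 responses and X₂ the responses among the next 15:

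P(success | p) = Σ over x = 6 to 13 of P(X₁ = x) × P(X₂ ≥ 15 − x)

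P(early stop | p) = P(X₁ ≤ 5)

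| Quantity | Stated | Recomputed |
|---|---|---|
| Significance level, p = 0.40 | 0.093 | 0.0930 |
| Power, p = 0.65 | 0.904 | 0.9035 |
| Early stop, p = 0.40 | 0.57 | 0.574 |
| Early stop, p = 0.65 | 0.05 | 0.046 |

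All four reproduce. None depends on the progression definition.

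**4. Size for PFS and duration of response.** The documents give no rate for progression confined to the uncovered sites, so what follows is illustration only. Let f be the assumed share of progressions of this type and d the assumed delay in recording them. The overstatement of mean time to progression is f × d.

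| f | d = 6 months | d = 12 months |
|---|---|---|
| 5% | 0.05 × 6 = 0.3 | 0.05 × 12 = 0.6 |
| 10% | 0.10 × 6 = 0.6 | 0.10 × 12 = 1.2 |
| 20% | 0.20 × 6 = 1.2 | 0.20 × 12 = 2.4 |

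The delays come from the CT schedule in 10.3 and 11.1: every 6 months for 2 years, then yearly. An event missed at the first restaging could be picked up sooner, since 11.1 places the two PET-CT assessments near days 84 and 168, which is 84 days or 12 weeks apart. An event never picked up has a longer effect than the table shows.

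In subjects: if all 28 progressed, 5% to 10% would be 0.05 × 28 = 1.4 to 0.10 × 28 = 2.8. One event moves the PFS curve by 1/28 = 3.6 percentage points with all 28 at risk and none censored. For duration of response, with about 0.65 × 28 ≈ 18 responders, one event is 1/18 = 5.6 points.

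**The case against.** **The cited 2014 criteria may fill the gap.** This is the strongest reply. Sections 11.1 and 13.1 invoke them, and assessors may apply an organ rule that 11.5.4 does not print. Their content cannot be checked from these documents. But 11.2 points to the protocol's own definitions, and nothing says that the citation supplements or overrides 11.5.4. At best, two assessors could date the same event differently, so the reply does not remove the need for a clarification.

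**Stable disease may not fit either.** For variably avid or PET-negative disease, 11.5.3 also describes stable disease as unchanged lesion size on CT, which a growing involved spleen does not plainly satisfy. That is a fair reading, but it leaves the subject unclassified rather than progressed, so the event is still not dated.

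**Exposure is limited.** This stands. Splenic marginal zone lymphoma requires prior splenectomy (3.1.1), every subject must have measurable disease (3.1.3), concurrent nodal growth still triggers progression, and death still ends PFS. Follicular and other marginal zone subjects keep the spleen, however, and liver and non-measurable sites matter for everyone.

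**A reader might infer that growth confined to the spleen, liver or non-measurable sites is never progression.** The documents do not support that. Item 2 catches measurable nodules in either organ, and item 1 catches new PET-positive lesions over 1.5 cm anywhere. Nor do both response rules name both organs: the CR rule names the spleen only, and liver size enters through the PR rule.

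**Conclusion.** The gap is real but narrow. As written, 11.5.4 cannot register diffuse spleen or liver enlargement without a measurable lesion, or worsening of existing non-measurable disease, while 11.5.1 and 11.5.2 use organ size to withhold response. Where that is a subject's only change, PFS and duration of response are dated late. The direction is certain provided the printed text is followed, because an unrecorded progression can only lengthen these times.

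The size is unknown and probably small. The range of 0.3 to 2.4 months rests wholly on assumed shares of 5% to 20% and assumed delays of 6 to 12 months. A reader might infer that the trial's PFS will be materially inflated or its main conclusion put at risk. The documents support neither: they give no frequency for such events, both endpoints are secondary with no stated test, and the Simon design for ORR does not depend on this definition. It is a correction worth making, not a threat to the design.

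**What to change.** For the purpose of dating PFS and duration of response, add an item to 11.5.4 along these lines: *an increase in spleen or liver size from the smallest prior size, or an increase in existing non-measurable disease of the kinds listed in 11.3, attributed to lymphoma by the imaging core; the event is dated at that scan.*

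State also that the 2014 criteria cited in 11.1 and 13.1 govern the size threshold and any point on which 11.5.4 is silent. The sponsor should confirm that the cited publication does supply a threshold before relying on it, since without one the new item would be open-ended.

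The wording must then be reconciled with the cycle 2 rule in 5.1 and the off-therapy criteria in 5.4, which use the same term. How those treatment rules should read is for the sponsor and investigator and is not proposed here.

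The cost is one item and one sentence. Spleen and liver are already on every scheduled CT. The downside is some added reader judgement in an open-label, single-arm trial, which central attribution and a stated threshold would limit.

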11.6 Duration of Response

Duration of overall response: The duration of overall response is measured from the time measurement criteria are met for CR or PR (whichever is first recorded) until the first date that recurrent or progressive disease is objectively documented (taking as reference for progressive disease the smallest measurements recorded since the treatment started).

The duration of overall CR is measured from the time measurement criteria are first met for CR until the first date that recurrent disease is objectively documented.

Duration of stable disease: Stable disease is measured from the start of the treatment until the criteria for progression are met, taking as reference the smallest measurements recorded since the treatment started.

11.7 Progression-Free Survival (PFS)

PFS is defined as the duration of time from start of treatment to time of documentation of progression or death.

11.8 Time to relapse (TTR) -

12. DATA REPORTING / REGULATORY REQUIREMENTS

Adverse event lists, guidelines, and instructions for AE reporting can be found in Section 7.0 (Adverse Events: List and Reporting Requirements).

12.1 Data Reporting

12.1.1 Method

The QACT will collect, manage, and perform quality checks on the data for this study.

12.1.2 Responsibility for Data Submission

:
Investigative sites within DF/HCC or DF/PCC are responsible for submitting data and/or data forms to the QACT according to the schedule set by the QACT.

12.2 Data Safety Monitoring

The DF/HCC Data and Safety Monitoring Committee (DSMC) will review and monitor toxicity and accrual data from this study. The committee is composed of clinical specialists with experience in oncology and who have no direct relationship with the study. Information that raises any questions about participant safety will be addressed with the Overall PI and study team.

The DSMC will review each protocol up to four times a year or more often if required to review toxicity and accrual data. Information to be provided to the committee may include: up-to-date participant accrual; current dose level information; DLT information; all grade 2 or higher unexpected adverse events that have been reported; summary of all deaths occurring within 30 days of intervention for Phase I or II protocols; for gene therapy protocols, summary of all deaths while being treated and during active follow-up; any response information; audit results, and a summary provided by the study team. Other information (e.g. scans, laboratory values) will be provided upon request.

12.3 Multicenter Guidelines

N/A

12.4 Collaborative Agreements Language

N/A

13. STATISTICAL CONSIDERATIONS

13.1 Study Design/Endpoints

Primary

- Overall Response Rate by the revised response criteria for malignant lymphoma (2014)

Secondary

- Clinical: Duration of response, time to response, progression-free survival, and overall survival
- Safety: Discontinuation of drug due to toxicity, adverse events

Exploratory

- Association of response and CNS toxicity with B:T lymphocytes ratio in peripheral blood
- Association of MRD status with progression free and overall survival

13.2 Sample Size, Accrual Rate and Study Duration

We will use a Simon two-stage design to assess whether the results of this regimen are consistent

with an overall response rate of 65%, which serves as our alternative hypothesis. We have identified an ORR of 40% as the null hypothesis. We will initially enroll 13 subjects. If 6 or more subjects achieve a response, we will enroll an additional 15 subjects. If 15 or more subjects of 28 achieve a response, we will consider the regimen worthy of further study. The probability that we observe 15 or more responses if the true but unknown response rate is 40% is 0.093; this serves as the significance level of the test. The probability that we observe 15 or more responses if the true but unknown ORR rate is 65% is 0.904, which serves as the power of the test. The study will stop early under the null hypothesis of 40% with probability 0.57 and under the alternative hypothesis of 65% with probability 0.05. It is anticipated that a minimum of 8-10 subjects will enroll per year with enrollment completing with in 3 years. Subjects without progressive disease will be followed for a total of 5 years with an anticipated study duration of 8 years.

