2.4 Correlative Studies Background

2.4.1 Neurologic toxicity

Patients receiving blinatumomab may experience a spectrum of neurologic events, the most clinically relevant being encephalopathy, confusional and cognitive disorders, memory impairment, disorientation, convulsions (convulsion, grand mal seizure, and epilepsy), speech disorders (aphasia, speech disorder, and dysarthria), cerebellar syndrome, tremor, and hallucinations. Across all indications/studies, the incidence of patients experiencing neurologic events is greatest within the first few days of blinatumomab treatment. Most of these events are clinically manageable after interruption or permanent discontinuation of blinatumomab. Of the 477 subjects enrolled across the program as of 10 October 2013, 243 patients (51%) have experienced neurologic TEAEs, and 197 (41%) were considered by the investigator as related to treatment. The majority of TEAEs occurred within the first week of the first cycle of blinatumomab treatment. Overall, the types of events observed in the R/R ALL population were similar to those in the MRD-positive and R/R NHL populations, with no major differences in the frequencies of events between indications. Serious neurologic events were observed at blinatumomab doses ranging from 5 to 90 μ g/m2/day, with higher doses (60 and 90 μ g/m2/day) associated with an increased severity of events in the NHL studies. Prodromal symptoms included tremor and disorientation. No specific pattern was observed in medical histories or concomitant medications. A baseline B cell to T cell (B:T) ratio in peripheral blood at or below 1:10 has been identified as a predictive factor for occurrence of neurological AEs.(13) We will correlate baseline B cell to T cell (B:T) ratio in peripheral blood measured by flow cytometry with neurologic events in a descriptive manner.

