5. TREATMENT PLAN

5.1 Treatment Regimen

This will be an open label single arm phase II study employing a Simon's optimal two stage design to assess efficacy and safety of blinatumomab in indolent NHL. Blinatumomab will be administered as a continuous IV infusion through a central venous catheter for a 42 day cycle. Blinatumomab will start with a 7 day infusion at 9mcg/d. If no dose limiting toxicity (table 6.1)

after 7 days, the dose will be escalated to 28 mcg/d for 7 additional days. If no dose limiting toxicity (table 6.1) after 14 days, blinatumomab will be infused at a target dose of at 112mcg/d for 28 days. The first 5 patients enrolled on study will be admitted for 3 days during each dose escalation as well as the first 3 days of cycle 2 to monitor for cytokine release syndrome as well as neurotoxicity. If no grade 4 toxicities are seen, future patients enrolled on study will begin therapy as an outpatient. Subjects will be restaged after a 6 week treatment free period by PET CT. All subjects without disease progression will receive an additional 4 week cycle starting at the target dose of 112 mcg/d. All subjects will then have an end of treatment PET CT 6 weeks after completion of the second infusion. All subjects with a response will then be followed with a CT every 6 months for the first 2 years and then annually for 5 years or until progression.

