6. DOSING DELAYS/DOSE MODIFICATIONS

6.1 Toxicity Management/ Dosage Adjustments

Table 6-1 Criteria for dosing delays and re-initiation of treatment for toxicity definitely or possibly related to study drug. Based on the Common Terminology Criteria for Adverse Events (CTCAE) version 4.0.

Toxicity	Grade	Action
Cytokine Release Syndrome (CRS)	Grade 3	Withhold blinatumomab until resolved to \leq grade 1, then restart blinatumomab at 9 mcg/day with dexamethasone 8mg TID for three days. Dexamethasone will then be decreased by 25% per day until discontinued. Escalate to 28 mcg/day after 7 days and then to 112 mcg/d after an additional 7 days if the toxicity does not recur.
	Grade 4	Remove from study
Neurologic toxicity	Seizure	Discontinue blinatumomab permanently if more than one seizure occurs despite antiepileptics.
	Grade 3	Withhold blinatumomab until \leq grade 1, (mild), then restart blinatumomab at 9 mcg/day with dexamethasone (or equivalent) 20mg iv within 1 hour of start of retreatment. Dexamethasone will then be decreased by 25% per day until discontinued. Escalate to 28 mcg/day after 7 days and then to 112 mcg/d after an additional 7 days if the toxicity does not recur. If the toxicity occurred at 9 mcg/day, or if the toxicity takes more than 7 days to resolve, discontinue blinatumomab permanently
	Grade 4	Remove from study
Other clinically relevant adverse reactions	Grade 3	Withhold blinatumomab until \leq grade 1 (mild), then restart blinatumomab at 9 mcg/day. Escalate to 28 mcg/day after 7 days and then to 112 mcg/d after an additional 7 days if the toxicity does not recur. If the toxicity occurred at 9 mcg/day, or if the toxicity takes more than 7 days to resolve, discontinue blinatumomab permanently
	Grade 4	Remove from study

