7.3 Expedited Adverse Event Reporting

7.3.1 Investigators **must** report to the Overall PI any serious adverse event (SAE) that occurs after the initial dose of study treatment, during treatment, or within 30 days of the last dose of treatment on the local institutional SAE form.

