7.6 Routine Adverse Event Reporting

All Adverse Events **must** be reported in routine study data submissions to the Overall PI on the toxicity case report forms. **AEs reported through expedited processes (e.g., reported to the IRB, FDA, etc.) must also be reported in routine study data submissions.**

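### Stage 2 opens on the response count alone: no DSMC toxicity review is tied to that step, and no event count pauses accrual

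*Combined protocol and SAP*

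**What the plan says.** Section 13.2 enrols 13 subjects first. The step to stage 2 depends on responses only: "If 6 or more subjects achieve a response, we will enroll an additional 15 subjects". Section 13.1 lists safety as a secondary endpoint, with no decision rule attached.

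Section 12.2 provides the oversight. The DSMC "will review and monitor toxicity and accrual data from this study", and the timing is: "The DSMC will review each protocol up to four times a year or more often if required to review toxicity and accrual data". No minimum frequency is given, and neither stage 1 nor stage 2 is mentioned. Safety questions are taken up with the Overall PI and study team; no action on accrual is named.

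Other safeguards are in place:
- Investigators must "report to the Overall PI any serious adverse event (SAE) that occurs after the initial dose of study treatment" (7.3.1), and all adverse events must "be reported in routine study data submissions to the Overall PI on the toxicity case report forms" (7.6).
- Table 6-1, headed "Criteria for dosing delays and re-initiation of treatment for toxicity definitely or possibly related to study drug", withholds, restarts or stops drug for the individual subject. Section 5.4 also acts on individuals.
- Under 5.1 the first 5 subjects are admitted around each dose escalation and at the start of cycle 2. The check that follows concerns the place of treatment: "If no grade 4 toxicities are seen, future patients enrolled on study will begin therapy as an outpatient".

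On dose, 2.2.5 equates the 112 mcg/d target with 60 mcg/m²/d. Section 2.4.1 says that the 60 and 90 mcg/m²/d levels were "associated with an increased severity of events in the NHL studies".

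**The concern.** Each safeguard acts on one subject, on the setting of care, or at a time left to discretion. If severe neurologic toxicity at the target dose were clearly more frequent than expected, every affected subject would be managed under Table 6-1. Nothing in the text, however, would require anyone to look at the cohort before the next subject, or the next 15, were dosed.

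The response gate is not a dependable substitute. Under 11.2 and 13.3.2, a subject who leaves for toxicity before completing cycle 1, without progression, is not evaluable for response, and the text does not say that such a subject counts as a non-responder. Early toxic withdrawals may therefore drop out of the count that opens stage 2. Section 2.4.1 places most neurologic events in the first week of cycle 1.

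Nor does the DSMC packet guarantee sight of these events. Section 12.2 says that it may include DLT information, unexpected grade 2 or higher events, and deaths within 30 days. Neurologic toxicity and CRS are listed as expected in 7.1, so the unexpected-event item need not capture them, and the DLT item is optional.

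**Working it through.** **1. The plan's own figures.** Inputs from 13.2: n1 = 13, continue with ≥6 responses; n = 28, success with ≥15; null ORR 40%, alternative 65%.

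P(success) = Σ over x = 6 to 13 of P(X1 = x) × P(Bin(15, p) ≥ 15 − x).

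This gives 0.0930 at 40% and 0.9035 at 65%. P(early stop) = P(Bin(13, p) ≤ 5) = 0.574 and 0.046. The stated 0.093, 0.904, 0.57 and 0.05 are reproduced, and the efficacy rule is not in dispute. Stage 2 therefore opens with probability 1 − 0.574 = 0.426 at ORR 40% and 1 − 0.046 = 0.954 at ORR 65%, whatever the toxicity count, provided toxicity does not change the response count.

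**2. Background event rates in the protocol.** Grade ≥3 neurologic toxicity is about 15% across blinatumomab trials (7.1.2). Grade ≥3 nervous system disorders occurred in 22/95 = 23.2% of NHL patients (Table 2-4; exact 95% CI 15.1% to 32.9%). Grade ≥3 CRS was 0/95 in NHL. The 23.2% is all-cause, pools several doses, and is a system-organ-class total that includes headache and tremor, so it is only a proxy for related events at 112 mcg/d. At that rate the expected number of affected subjects is 13 × 0.232 = 3.0 in stage 1 and 28 × 0.232 = 6.5 overall.

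**3. What a count rule could do (illustration).** The protocol gives no unacceptable rate, so the boundary here is an assumption: pause on reaching 3 affected within the first 5 treated, 6 within 13, 8 within 20 or 10 within 28, checked after every subject. Exact binomial recursion, with all 28 enrolled:

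| True event rate | P(pause by subject 13) | P(pause by subject 28) |
|---|---|---|
| 15% | 0.031 | 0.036 |
| 20% | 0.074 | 0.102 |
| 23.2% | 0.116 | 0.178 |
| 30% | 0.246 | 0.420 |
| 40% | 0.507 | 0.796 |

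Over the interval for 22/95, P(pause) runs from 0.04 to 0.54.

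The last column assumes that stage 2 opens. With toxicity independent of response and ORR 40%, the figure at a 40% event rate is 0.507 + 0.426 × (0.796 − 0.507) = 0.63. At ORR 65% it is 0.507 + 0.954 × (0.796 − 0.507) = 0.78.

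**4. Effect on power.** A pause for review leaves alpha and power as stated. In the worst case, where every pause closes the trial and toxicity is independent of response, power = 0.9035 × (1 − P(pause)):
- 15%: 0.9035 × 0.964 = 0.87
- 23.2%: 0.9035 × 0.822 = 0.74
- 30%: 0.9035 × 0.580 = 0.52

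Alpha can only fall.

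**5. Would a review happen anyway?** At the 8 to 10 subjects a year in 13.2, stage 1 accrual takes 13/10 to 13/8 years, or 15.6 to 19.5 months. With reviews up to four times a year, one before stage 2 is likely, though not required.

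**The case against.** The strongest reply is that oversight is already adequate. The DSMC may meet more often if required, may receive DLT information and death summaries, and can raise a safety question at any time. SAEs go to the Overall PI, who as study sponsor also reports to the FDA (7.4). Section 13.2 is an efficacy rule that runs beside 12.2, and nothing in it overrides the DSMC. All of this stands. A reader might infer that the trial has no safety oversight, or that stage 2 must open despite known harm; the documents support neither. What remains is that the timing of review is discretionary and no count forces one.

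A second reply is that any boundary is the reviewer's choice and that the one shown is not sharp: at a true rate of 30% it fails to trigger in 58% of trials of 28, and at 40% it triggers within the first 13 only about half the time. That also stands. It is why the boundary is offered only as an illustration, and why the stage 1 review, which does not depend on a count, comes first.

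A reader might also be tempted to count subjects dosed after such a boundary as exposures that the rule would avoid. That is not supported. It would assume that all 28 enrol and that the DSMC never acts unprompted, and it would treat a pause as closure.

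**Conclusion.** The gap is real and modest. Stage 2 opens on responses alone, no DSMC review is tied to that step, and no event count pauses accrual. This is a missing rule, not a numerical error, and closing it is a cheap safety improvement. The required review mainly turns a likely event into a certain one. The pause count adds a prompt whose strength depends on the boundary chosen: for the illustration, 0.04 at 15% and 0.80 at 40% if all 28 enrol. These figures rest on independent subjects, a constant event rate and an assumed boundary. The 23.2% rate is a proxy, so the 0.18 attached to it is uncertain.

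**What to change.** In 12.2 and 13.2:

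1. Require the existing DSMC to review stage 1 toxicity before any stage 2 subject is dosed. This is one sentence and is the smallest useful change.
2. Pause accrual for DSMC review, not automatic closure, when the number of subjects with related grade ≥3 neurologic toxicity or related grade ≥3 CRS reaches a sponsor-set count, checked continuously. The boundary 3/5, 6/13, 8/20, 10/28 is one example.
3. State the unacceptable rate behind the count and print the boundary's operating characteristics. If a rate near 23% is acceptable, a looser boundary may be preferable.

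Table 6-1 and the Simon rule stay as they are.

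The cost is a protocol amendment, using the existing committee and adverse event data already collected. If accrual waits for subject 13's day 84 scan (11.1), the review can be done in the 6 weeks between the end of that subject's first infusion and the scan. The downside is a possible short accrual pause (probability 0.04 at a 15% event rate and 0.18 at 23.2% for the example boundary). Power is lost only if the DSMC then closes the trial.
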